### — Contraception for Female Subjects of Childbearing Potential

The inclusion of female subjects of childbearing potential requires the use of highly effective contraceptive measures. Women must have a negative pregnancy test at the Day 1 visit of the LTE. Pregnancy tests will be performed at monthly intervals thereafter. In the event of a delayed menstrual period (> one month between menstruations), a pregnancy test must be performed to rule out pregnancy. This is true even for women of childbearing potential with infrequent or irregular periods.

Female subjects must agree to continue to use one of the following methods from Screening (parent study) until 30 days following the last dose of study drug.

- Complete abstinence from intercourse of reproductive potential. Abstinence is an acceptable method of contraception only when it is in line with the subject's preferred and usual lifestyle.

Or

- Consistent and correct use of 1 of the following methods of birth control listed below.
  - Intrauterine device (IUD) with a failure rate of < 1% per year
  - Tubal sterilization
  - Essure micro-insert system (provided confirmation of success 3 months after procedure)
  - Vasectomy in the male partner (provided that the partner is the sole sexual partner and had confirmation of surgical success 3 months after procedure)

Female subjects, who wish to use a hormonally based method, must use it in conjunction with a barrier method; the barrier method is to be used either by the female subject or by her male partner. Female subjects who utilize a hormonal contraceptive as one of their birth control methods must have consistently used the same method for at least three months prior to study dosing. Hormonally-based contraceptives and barrier methods permitted for use in this protocol are as follows:

- Hormonal methods (each method *must* be used with a barrier method, preferably male condom)
  - Oral contraceptives (either combined estrogen/progestin or progesterone only)
  - Injectable progesterone
  - Implants of levonorgestrel
  - Transdermal contraceptive patch
  - Contraceptive vaginal ring

- Barrier methods (each method *must* be used with a hormonal method)
  - Male or female condom with or without spermicide
  - Diaphragm with spermicide
  - Cervical cap with spermicide
  - Sponge with spermicide

All female subjects must also refrain from egg donation and in vitro fertilization during treatment and until at least 30 days after the last study drug dose.

- **Unacceptable Birth Control Methods**

Birth control methods that are unacceptable include periodic abstinence (eg, calendar, ovulation, symptothermal, post-ovulation methods), withdrawal (coitus interruptus), spermicides only, and lactational amenorrhea method (LAM). Female condom and male condom should not be used together.

- **Procedures to be Followed in the Event of Pregnancy**

Subjects will be instructed to notify the investigator if they become pregnant at any time during the study, or if they become pregnant within 30 days of last study drug dose. Subjects who become pregnant or who suspect that they are pregnant during the study must report the information to the investigator and discontinue study drug immediately.

Instructions for reporting pregnancy and pregnancy outcome are outlined in Section [7.7.2.1](#).

- **Pregnancy Testing**

All females of childbearing potential will have urine pregnancy testing every 4 weeks during their study participation. The test will be performed at home or in the clinic if it coincides with a scheduled visit. In case of home urine pregnancy testing, the site will contact the subject to obtain the results and will record the information in the eCRF. For subjects in the US, all pregnancy tests will be carried out in the clinic. If a urine pregnancy test is positive, the subject should stop study drug immediately, contact the investigator, and have confirmatory serum pregnancy test in clinic.

**Appendix 7. Clinical Laboratory Assessment Table**

Hematology	Chemistry	Urinalysis	Other
Hematocrit Hemoglobin Platelet count Red blood cell (RBC) count White blood cell (WBC) count Differentials (absolute and percentage), including: Lymphocytes Monocytes Neutrophils Eosinophils Basophils Reticulocyte count Mean corpuscular volume (MCV)	Alkaline phosphatase Aspartate aminotransferase (AST) Alanine aminotransferase (ALT) Total bilirubin Direct and indirect bilirubin Total protein Albumin Bicarbonate Blood urea nitrogen (BUN) Calcium Chloride Serum creatinine Creatinine clearance CC&G Glucose Phosphorus Magnesium Potassium Sodium Creatine Phosphokinase (CPK)	Appearance: Blood Color Glucose Leukocyte esterase pH Protein Urobilinogen	██████████ (████) ██████████ ██████████ ██████████ ██████████ Bacterial stool culture C-diff toxin Ova and parasites (O&P)
	Fasting Lipids	Pregnancy	
	Triglycerides Cholesterol and its subfractions (high-density lipoprotein [HDL] and low density lipoprotein [LDL])	In females of childbearing potential: Urine pregnancy Serum pregnancy	██████████ ██████████ ██████████ Serum Immunoglobulin QuantiFERON® (or centrally reported equivalent assay) Prothrombin time (PT) Partial Thromboplastin time (PTT) International Normalized Ratio (INR) HBV DNA

Signature Page for glpg0634-cl-310-protocol-amend9 21162

Approval	 24-Nov-2022 13:48:54 GMT+0000
----------	---

Signature Page for glpg0634-cl-310-protocol-amend943952\_40834\_108642

CTCAE	Common Terminology Criteria for Adverse Events
CV	cardiovascular
CVEAC	cardiovascular safety endpoint adjudication committee
DMC	data monitoring committee
ECG	electrocardiogram
eCRF	electronic case report form
ET	early termination
Hb	hemoglobin
HDL	high-density lipoprotein
HLGT	high-level group term
HLT	high-level term
ID	identification
Ig	immunoglobulin
LDL	low-density lipoprotein
LOQ	limit of quantitation
LTE	long term extension
LTT	lower-level term
MACE	major adverse cardiovascular events
MedDRA	Medical Dictionary for Regulatory Activities
MI	myocardial infarction
MST	MedDRA search term
NLP	Natural Language Processing

PRO2	patient reported outcome consisting of 2 items: abdominal pain severity and liquid stool frequency
PT	preferred term
PTx	post-treatment
Q1	first quartile
Q3	third quartile
SAE	serious adverse event
SAP	statistical analysis plan
SD	standard deviation
SE	standard error
████	████████████████████
SMQ	Standardized MedDRA Query
SOC	system organ class
TE	treatment-emergent
TEAE	treatment-emergent adverse event
TFLs	tables, figures, and listings
ULN	upper limit of normal
V-Day	visit day
VAS	Visual Analogue Scale
VTE	venous thromboembolism
WHO	World Health Organization
████	████████████████████

1. INTRODUCTION

This statistical analysis plan (SAP) describes the statistical analysis methods and data presentations to be used in tables, figures, and listings (TFLs) in the interim analyses and clinical study report (CSR) for Study GS-US-419-3896 (GLPG0634-CL-310). This SAP is based on the study protocol Amendment 8 dated 2 December 2021 and the electronic case report form (eCRF). The SAP will be finalized before unblinding of Study GS-US-419-3895 (GLPG0634-CL-309), at which time this study will be unblinded. Any changes made after the finalization of the SAP will be documented in the CSR.

1.1. Study Objectives

The primary objective of this study is:

- To observe the long-term safety of filgotinib in subjects who have completed or met protocol specified efficacy discontinuation criteria in a prior filgotinib treatment study for Crohn's disease (CD)

The secondary objective of this study is:

- To evaluate the effect of filgotinib on Patient Reported Outcomes (PRO2) and Crohn's Disease Activity Index (CDAI) scores

[REDACTED]

[REDACTED]

[REDACTED]

[REDACTED]

[REDACTED]

[REDACTED]

1.2. Study Design

This is a long-term extension (LTE) study to evaluate the safety of filgotinib administered to subjects with CD. Some subjects will receive open-label drug and some will continue to receive the blinded study drug assigned in the parent study until subject's treatment in the corresponding parent study (GS-US-419-4015, GS-US-419-4016, or GS-US-419-3895) is unblinded. The duration of treatment is up to 432 weeks.

In general, subjects who fully complete a parent study blinded will continue blinded treatment at the same regimen in the present study on 200 mg filgotinib, 100 mg filgotinib, or placebo. Subjects who enroll from a parent study and receive blinded treatment in the GS-US-419-3896 study will have their GS-US-419-3896 treatment assignment unblinded when the parent study is unblinded. After the study unblinding, subjects will continue on the same dose of open-label filgotinib as they had been receiving in blinded treatment; whereas subjects on placebo treatment

will discontinue study drug and study participation. Subjects who exit a parent study due to disease worsening or failure to meet response or remission criteria will receive open-label 200 mg filgotinib, with the exception of US and Korea males in this category who were not considered biologic refractory who will receive open-label 100 mg filgotinib.

This study includes:

- Day 1
- Treatment Visits: Week 2, Week 4, Week 12, and then every 12 weeks thereafter
- Post-Treatment (PTx) safety assessments (30 days after the last dose of study drug) for subjects who complete all study treatment visits or discontinue early

For additional details, please see the Schedule of Assessments in [Appendix 1](#).

1.3. Sample Size and Power

No formal hypothesis testing is planned for this study and sample size calculation is not conducted. All subjects who have completed or met protocol-specified efficacy discontinuation criteria in a parent study (GS-US-419-4015, GS-US-419-4016, or GS-US-419-3895) may enroll in this study. The projected number of subjects enrolled is approximately 1000.

2. TYPE OF PLANNED ANALYSIS

2.1. Interim Analyses

Prior to the final analysis, interim analyses may be performed for regulatory submission and/or for publication purposes. The first interim analysis is planned to align with the final analysis of Study GS-US-419-3895, at which time this study will be unblinded.

Interim analyses may present a subset of the analyses included in this analysis plan.

2.2. Final Analysis

The final analysis will be performed after all subjects have completed the study.

3. GENERAL CONSIDERATIONS FOR DATA ANALYSES

All analyses described in this SAP will include data from the LTE study (GS-US-419-3896) exclusively, not from the corresponding parent studies, except for subgroup analyses based on parent study completion status. Consequently, any reference to study drug (e.g., first dosing date) implies study drug administered in Study GS-US-419-3896, unless specifically stated otherwise.

Analysis results will be presented using descriptive statistics. For categorical variables, the number and percentage of subjects in each category will be presented; for continuous variables, the number of subjects (n), mean, standard deviation (SD) or standard error (SE), median, first quartile (Q1), third quartile (Q3), minimum, and maximum will be presented.

By-subject listings will be presented for all subjects in the All Enrolled Analysis Set and sorted by subject identification (ID) number, visit date, and time (if applicable). Data collected on log forms, such as adverse events (AEs), will be presented in chronological order within the subject. The treatment group to which subjects were assigned at enrollment will be used in the listings. Age (on the first dosing day in the LTE), sex at birth, race, and ethnicity will be included in the listings, as space permits.

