### **LTE Day 1 Rollover from any other filgotinib treatment study for CD**

Subjects that have completed\* a Gilead/Galapagos-sponsored parent study may enter this study up to 30 days after completing the end of study procedures in the parent study. After LTE consent is obtained, complete all Day 1 LTE procedures.

\*A subject is defined as completed if they have completed all study visits and procedures as defined in the protocol or have completed treatment up to the primary endpoint.

Please refer to the Phase 2 studies' subject rollover manual for details on rollover procedures.

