- a Day 1 visit for this study may occur at the same time as the final scheduled treatment visit of the prior filgotinib study or up to 30 days after completing the end of study procedures in the parent study, see Section 6.2.1. All procedures necessary for the final visit in the prior filgotinib study will be completed as well as any additional procedures required for this study. Procedures that are duplicates of the final visit from prior filgotinib study do not need to be performed again for this protocol. Day 1 may be delayed up to 10 days. If Day 1 of LTE is not the same as the last study visit of the prior study, a full set of Day 1 procedures should be performed. If a subject has already taken study drug for that day within the parent protocol, first dose should take place on Day 2.
- b The Post-Treatment (PTx) Visit should occur 30 days after the last dose of study drug.
- c The perianal fistula assessment entails tracking the clinical status of draining external openings of perianal fistulae that were identified at baseline of Study GS-US-419-4016. For additional details on the perianal assessment, refer to the Perianal Fistula Assessment Manual
- d Vital signs include resting blood pressure, respiratory rate, pulse, and temperature.
- e Fasting means no food or drink except water, for 8 hours
- f Females who are of childbearing potential only. A urine pregnancy test must be completed every 4 weeks at a minimum. The test will be performed at home or in the clinic if it coincides with a scheduled visit. In case of home urine pregnancy testing, the site will contact the subject to obtain the results and will record the information in the eCRF. For subjects in the US, all pregnancy tests will be carried out in the clinic. If any pregnancy test is positive, study drug should be immediately interrupted and the subject should have a serum pregnancy test in clinic.
- g In Japan, subjects with negative HBsAg, positive HBcAb and/or positive HBsAb in a parent CD protocol require HBV DNA monitoring every 4 weeks in accordance with local guidelines (Section 6.2.1).
- h In other regions, subjects with negative HBsAg and positive HBcAb require HBV DNA monitoring every 3 months in accordance with local guidelines (Section 6.2.1)
- i Subjects who were previously treated for TB do not need to have yearly QuantiFERON® (or centrally reported equivalent assay) tests but should be screened at least yearly for signs and symptoms of reactivation.
- j [REDACTED]

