- k [REDACTED]
- l At Day 1 visit, review diary of subject reported components from parent study, if available. Subjects should begin filling out the Diary at the Day 1 visit and continue to fill it out throughout the study.
- m Colonoscopy with biopsies is optional per standard of care. The date of the procedure may be requested for accuracy of data analysis.
- n [REDACTED]
- o Ongoing AEs from previous filgotinib studies should be recorded as medical history. Collection of AEs and SAEs related to protocol-mandated procedures will begin once informed consent is signed and will continue through the Post-Treatment (PTx) Visit.

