3.8.4. Definition of Baseline

Baseline in the LTE is defined as the last nonmissing value on or prior to the first dosing date of study drug in Study GS-US-419-3896, unless specified differently. If there are multiple records with the same time or no time recorded on the same day, the baseline value will be the average of the measurements for continuous data, or the measurement with the lowest severity (eg, normal will be selected over abnormal for safety electrocardiogram [ECG] findings) for categorical data.

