 - c The perianal fistula assessment entails tracking the clinical status of draining external openings of perianal fistulae that were identified at baseline of Study GS-US-419-4016 . For additional details on the perianal assessment, refer to the Perianal Fistula Assessment Manual
 - d Vital signs include resting blood pressure, respiratory rate, pulse, and temperature.
 - e Fasting means no food or drink except water, for 8 hours
 - f Females who are of childbearing potential only. A urine pregnancy test must be completed in clinic every 4 weeks at a minimum. If any pregnancy test is positive, study drug should be immediately interrupted and the subject should have a serum pregnancy test in clinic.
 - g In Japan, subjects with negative HBsAg, positive HBcAb and/or positive HBsAb in a parent CD protocol require HBV DNA monitoring every 4 weeks in accordance with local guidelines (Protocol Section 6.2.1).
 - h In other regions, subjects with negative HBsAg and positive HBcAb require HBV DNA monitoring every 3 months in accordance with local guidelines (Protocol Section 6.2.1)
 - i Subjects who were previously treated for TB do not need to have yearly QuantiFERON® (or centrally reported equivalent assay) tests but should be screened at least yearly for signs and symptoms of reactivation.
 - j [REDACTED]
 - k [REDACTED]
 - l At Day 1 visit, review diary of subject reported components from parent study. Subjects should begin filling out the Diary on Day 1 visit and continue to fill it out throughout the study.
 - m Colonoscopy with biopsies is optional per standard of care. The date of the procedure may be requested for accuracy of data analysis.
 - n [REDACTED]
 - o Ongoing AEs from previous filgotinib studies should be recorded as medical history. Collection of AEs and SAEs related to protocol-mandated procedures will begin once informed consent is signed and will continue through the Post-Treatment (PTx) Visit.

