Calculation of CDAI and PRO2 Scores for Baseline and Post-baseline Visits

The calculations of CDAI and PRO2 scores for baseline and post-baseline visits are specified below:

- 1) The Day 1 visit date will be used as the anchor day for baseline and following visit dates will be used as the anchor day for post-baseline visits. The visit date for each analysis visit will be selected as the anchor day among all scheduled visits and unscheduled visits where CDAI were assessed within the analysis window as defined in Section 3.8.2. Only diary data collected on evaluable days within a 10-day window which starts 10 days prior to the selected visit date (V-Day 1) and ends on the day prior to V-Day 1 will be used for calculation.
- 2) If there are 7 or more evaluable records within the 10-day window, take the **sum** of the 7 evaluable records closest to V-Day 1 for the corresponding CDAI subject-reported component. For the corresponding PRO2 component, take the **average** of the 7 evaluable records within the 10-day window closest to V-Day 1.
 - a) If there are 4 or more (but less than 7) evaluable records within this 10-day window, the average of the available records will be taken, and then multiplied by 7 for the corresponding CDAI patient-reported component. For the corresponding PRO2 component, the average of the available records will be taken.
 - b) If subjects do not have at least 4 evaluable records within this 10-day window, the corresponding CDAI patient-reported component, and the corresponding PRO2 component will not be calculated and will be considered as missing for that visit.

A schema of this approach and some examples are included below for further explanation:

Figure 1. Selection of Diary Data for the Calculation for Baseline and Postbaseline Visits

[figure not shown]

Table 11-3. Calculation of CDAI Patient-Reported Outcome Components and PRO2 Scores for Baseline and Post-baseline Visits

Example	Diary Day Looking Backwards from Visit Date (V-Day)										Days for Calculation	Sum of 7 Days (CDAI Patient-Reported Component)	Average of 7 Days (PRO2)
	-10	-9	-8	-7	-6	-5	-4	-3	-2	-1			
Diary Subscore 1	1	2	2	M	0	1	2	2	1	X	-2,-3,-4,-5,-6,-8,-9	10.0	1.4
Diary Subscore 2	M	M	1	M	X	IL	2	2	1	M	-2,-3,-4,-8	10.5	1.5
Diary Subscore 3	M	M	1	X	IL	M	M	2	1	M	-2,-3,-8	Missing	Missing
Diary Subscore 4	0	M	2	2	1	0	M	2	X	IL	-3,-5,-6,-7,-8,-10	8.2	1.2

M = Missing; IL = Ileocolonoscopy day; X = non-evaluable (due to preparation for ileocolonoscopy).

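### Fasting lipids have no scheduled LTE baseline, yet the SAP plans lipid change from baseline and treatment-emergent lipid grading

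*SAP*

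**What the plan says.** **Data source.** SAP Section 3 states that every analysis uses data "from the LTE study (GS-US-419-3896) exclusively, not from the corresponding parent studies, except for subgroup analyses based on parent study completion status". The later qualifier in that section, allowing for statements to the contrary, applies only to references to study drug. SAP 3.8.4 sets baseline by time, not by source: "Baseline in the LTE is defined as the last nonmissing value on or prior to the first dosing date of study drug". SAP 7.2.1 does the same for laboratory values.

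**Lipid sampling.** The fasting lipid row in protocol Appendix 2 and in SAP Appendix 1 has a mark only in the column for every 24 weeks. Among the visit descriptions in protocol Section 6, only 6.3.4 (the 24-weekly visit) asks for fasting blood.

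**Lipid analysis.** SAP 7.2.1 plans baseline, post-baseline and change-from-baseline summaries for total cholesterol, LDL, HDL, triglycerides, non-HDL cholesterol and the LDL/HDL ratio, and line plots of change for the first three. SAP 7.2.2 grades laboratory results by CTCAE 4.03 and makes no exclusion for lipids. With a missing baseline, 7.2.2.1 counts any value of Grade 1 or higher as treatment-emergent, and 7.2.2.2 counts any Grade 3 or 4 value as marked. The denominator in 7.2.2.3 requires a post-baseline value only.

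**Diary baseline.** SAP Appendix 2 anchors baseline CDAI and PRO2 on the Day 1 visit: "Only diary data collected on evaluable days within a 10-day window which starts 10 days prior to the selected visit date (V-Day 1"), ending the day before that visit. SAP Appendix 1, footnote l, says of the LTE diary: "Subjects should begin filling out the Diary on Day 1 visit and continue to fill it out throughout the study".

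**The concern.** Change from baseline needs a value before the first LTE dose. For lipids the LTE schedules none, and Section 3 closes the only other source, the parent studies. Followed as written, the lipid change summaries and plots would be empty apart from any unscheduled pre-dose sample.

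The grading rules do more harm than the empty summaries, because they still produce numbers. With no baseline, a lipid abnormality carried into the LTE is tabulated as having emerged on LTE treatment, and the subject stays in the denominator. Laboratory tests are part of the primary safety endpoint (protocol 8.1.2). Protocol 1.4 also cites lipid effects in the earlier phase 2 study, including a rise in HDL, as a possible benefit, so readers are likely to look at these tables.

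The same Section 3 sentence touches the secondary endpoint. The baseline diary days all precede the Day 1 visit, so under the LTE-only rule none of them would count.

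**Working it through.** The plan gives no figure to reproduce here. The check sets the schedules beside the analysis rules.

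**1. Is there a lipid baseline in the LTE schedule?** Marks in protocol Appendix 2 and SAP Appendix 1:

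| Row | Day 1 | Repeat |
|---|---|---|
| Hematology, chemistry | yes | Weeks 2, 4, 12, then 12-weekly |
| Urinalysis | yes | 24-weekly |
| Serum immunoglobulin | yes | 24-weekly (this cell is blacked out in the SAP) |
| TB assessment | yes | 48-weekly |
| Fasting lipids | **no** | 24-weekly |

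Tests meant to be taken at Day 1 carry their own Day 1 mark, so the blank in the lipid row means something. The row is not redacted and reads the same in both documents. The first scheduled sample is at 24 × 7 + 1 = Study Day 169. With the ±7-day allowance that is Day 162 to 176, well after first dose. Scheduled LTE lipid baselines: 0.

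SAP Table 3-2 has a Baseline row, but lipids share that table with serum immunoglobulin, which does have a Day 1 sample. The row does not show that a lipid baseline exists.

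**2. How many planned summaries are affected?**
- Measures named in 7.2.1: 6.
- Post-baseline rows in Table 3-2: 432 / 24 = 18.
- Reachable rows: protocol 3.4 caps treatment at about 7.5 years, 7.5 × 365.25 ≈ 2,739 days. That falls in the Week 384 window (Days 2606 to 2773), and 384 / 24 = 16.
- Adding the 30 days after last dose gives 2,739 + 30 = 2,769, still inside that window.
- Result: 6 × 16 = 96 change-from-baseline summaries per treatment group. Three of the six measures are also plotted.

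**3. What do the grading rules do?** Let g be the true pre-LTE grade and m the worst post-baseline grade.
- Baseline known: treatment-emergent if m ≥ g + 1; marked if m ≥ g + 3.
- Baseline missing: treatment-emergent if m ≥ 1; marked if m ≥ 3.

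A subject at Grade 2 throughout (g = 2, m = 2) is not treatment-emergent under the first rule but is under the second. A subject at Grade 3 throughout becomes both treatment-emergent and marked.

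The wrongly labelled treatment-emergent share is p × q. Here p is the share of subjects at Grade 1 or higher before the LTE, and q is the share of those with 1 ≤ m ≤ g. Neither is given. Since q lies between 0 and 1, the excess lies between 0 and p. Wrongly labelled marked values also need g ≥ 1, so the same bound applies to them.

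**4. The diary baseline.** The window is V-Days −10 to −1, which is 10 days. The LTE diary starts on Day 1. LTE diary days in the window: 0, against a minimum of 4.

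**The case against.** **The missing-baseline rule is the protocol's own and is conservative.** This is true. Protocol 8.3 and 8.6.3 prescribe it and the SAP follows. It errs towards over-reporting, and departing from it would report fewer events. But the rule suits the occasional missing sample. Applied to a test with no scheduled baseline, it covers nearly every subject, and the label treatment-emergent loses its meaning.

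**A parent-study lipid panel may exist.** It may; the parent schedules are not in these documents, and 3.8.4 names no source study. Even so, Section 3 as written bars its use, so the SAP has to say that it is allowed.

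**The sponsor has already dealt with missing baselines.** In part. SAP Section 10 records that the ECG shift table gave way to a frequency table because no baseline ECG exists, and version 2.0 removed laboratory shift tables as unnecessary. The lipid change summaries and the treatment-emergent and marked tables remain.

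**Grading of lipids is not spelled out.** This stands as a limit. The documents show a graded lipid only for triglycerides, as an example in protocol 7.6.3. The grading concern covers whichever lipids CTCAE grades and no more.

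Three stronger readings are tempting and not supported:
- *That the secondary endpoint cannot be computed.* Protocol 6.2.1 has sites review the prior-study diary, and protocol Appendix 2, footnote l, says "At Day 1 visit, review diary of subject reported components from parent study, if available". Parent diary days were plainly meant to supply the baseline. The conflict is one of wording.
- *That the SAP is silent on subjects who enter late.* Protocol Appendix 2 says "Day 1 may be delayed up to 10 days", and subjects from other CD studies "may enter this study up to 30 days after completing the end of study procedures in the parent study". SAP Appendix 2 covers the result: "If subjects do not have at least 4 evaluable records within this 10-day window", the component is missing for that visit, baseline included. The number without a baseline is the group size minus the n in each summary. The 30-day route came with Amendment 9, whereas the SAP is based on Amendment 8. How many subjects would fall short cannot be worked out, because the documents do not say when the parent diary stops.
- *That all 18 windows, 6 × 18 = 108 summaries, are at stake.* The treatment limit reaches about 16.

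**Conclusion.** The lipid point holds and should be fixed. The LTE schedules no fasting-lipid sample before Week 24, Section 3 excludes parent data, and the SAP still plans about 96 lipid change-from-baseline summaries per treatment group plus three plots. For the lipids that CTCAE grades, abnormalities present before the LTE would be reported as treatment-emergent or marked. The size of that excess cannot be derived from the documents; it lies between 0 and the share of subjects already at Grade 1 or higher on entry.

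This rests on three conditions: Section 3 is applied as written, few or no unscheduled pre-dose fasting samples exist, and maximum treatment is about 7.5 years.

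The diary point is a minor clarification of Section 3. It does not put the secondary endpoint in doubt.

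**What to change.** **Lipids (SAP 3, 3.8.4 and 7.2).**
- Allow a parent-study fasting lipid panel dated on or before the first LTE dose to serve as baseline, if one exists. Prespecify its maximum age from the parent studies' lipid schedules, which these documents do not give.
- If no such panel exists, omit lipid change from baseline and the three change plots. Report the worst on-treatment lipid grade without the treatment-emergent or marked label, and state the number of subjects with no lipid baseline.
- Record this as a departure from protocol 8.3 and 8.6.3.

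**Wording (SAP 3).** Add that parent-study records dated on or before the first LTE dose may serve as LTE baseline. Include diary V-Days −10 to −1 and Day 1 assessments not repeated because they duplicated the final parent visit. The minimum of 4 evaluable diary records stays as it is, and no separate count table is needed.

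**Cost.** SAP 2.0 is final, so this needs an amendment or, as SAP Section 1 provides, documentation in the clinical study report. The programming is small: one relabelled lipid table and possibly some deleted output. The downside is fewer lipid change summaries, or none, and a documented departure from the protocol's conservative convention.
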